6.3 Run-in procedures

No run-in phase is planned for this study.

6.4 Contraindications

Contraindications to taking YF476 include prolonged QTc interval, pregnancy or breastfeeding. Patients with prolonged QTc interval (>450 msec) are excluded. Women of childbearing potential will be included in the study only if they are using adequate contraception and will be advised by the recruiting physician and in the information and consent form about the risks of becoming pregnant while taking part in the study. Pregnancy tests will be done at each visit.

6.5 Concomitant medications

All study patients will take proton pump inhibitors at least once daily. Any formulation of PPI is permitted during the study period.

All medications (prescription and over-the-counter), vitamin and mineral supplements, and/or herbs taken by the participant will be documented on the concomitant medication CRF and will include: 1) start and stop date, dose and route of administration, and indication. Medications taken for a procedure (eg: biopsy) should also be included.

CYP 450 enzymes

Studies were done to assess the potential of YF476 to inhibit cytochrome P450 enzymes *in vitro*. For details, see Appendix B – drug interactions, and the YF476 Investigator's Brochure. The likelihood of a drug-drug interaction in patients *in vivo* is:

- CYP2C8: possible for 50–400 mg YF476
- CYP3A4 (testosterone): remote for 50 & 100 mg YF476, and possible for 200 & 400 mg
- CYP3A4 (midazolam): remote for 50 mg YF476, and possible for 100–400 mg.

Although YF476 caused some irreversible inhibition of CYP3A4 *in vitro*, the degree of inhibition makes a drug-drug interaction in patients *in vivo* unlikely. And, a clinical study (T-007) of YF476 and midazolam (a substrate of CYP3A4) alone and in combination showed that neither medicine affects the pharmacokinetics of the other. For details, see the Netazepide (YF476) Investigator's Brochure.

Many medicines are metabolised via CYP3A4/5. Very few are metabolised via CYP2C8. Examples of the main types of medicine that are metabolised by CYP3A4/5 and CYP2C8 are listed in Appendix B. Guidance about assessing the risk and managing drug-drug interactions is also provided in Appendix B.

Drugs that are substrates for, or inhibitors or inducers of CYP3A4/5 and CYP2C8 are not prohibited, but the patients must be monitored carefully, and the investigator must be informed of any new concomitant medications via the patient's diary card. Midazolam may be used during endoscopy. It was used safely before gastroscopy in a study of YF476 in healthy subjects.

6.6 Dose modification

Dose modifications of study drug will not be performed. If drug-related toxicity is suspected, then treatment will be discontinued.

6.7 Compliance

- All randomized patients will be eligible for statistical analysis. Patients will be analyzed on an intent-to-treat basis, and also per protocol.

-
- Compliance will be measured by capsule counts at the Week 6 and Week 12 visits, and by review of patient diary cards.

[figure not shown]
7 Pharmaceutical information

YF476 (IND # 107354, IND Sponsor: Trio Medicines Ltd)

7.1 Active pharmaceutical ingredient (API): YF476

International non-proprietary name (INN): netazepide

Structural formula:

Chemical formula: (*R*)-1-[2,3-dihydro-2-oxo-1-pivaloylmethyl-5-(2-pyridyl)-1*H*-1,4-benzodiazepin-3-yl]-3-(3-methylaminophenyl)urea

Molecular formula: C₂₈H₃₀N₆O₃

Molecular weight: 498.58

Description: white crystalline powder

Purity: 99.9%

Optical rotation: [α]_{D20} = +124 ° (Acetone, 0.5%)

Acid dissociation constant (pKa): 2.53, 4.59

Hygroscopicity: <0.3% at room temperature, and 93% relative humidity (7 days)

Stability: Chemically stable for at least 9.5 years at room temperature, protected from light.

7.2 Formulated intermediate: spray-dried YF476

YF476 and hydroxypropylmethylcellulose (HPMC) (YF476:HPMC ratio 1:3.5) were dissolved in dichloromethane/isopropanol (7:2 v/v). The solution was spray-dried, and at all stages of production, the solution and resulting spray-dried powder were shielded from light. The formulated intermediate was characterised as follows.

Description: white to off-white powder

Structural configuration: amorphous by x-ray powder diffraction

YF476 purity: ≥95% of the theoretical purity (adjusted for water)

Water content: ≤7.5%

Residual dichloromethane: ≤ 2000 ppm

Residual isopropanol: ≤ 10000 ppm

Stability: Chemically and physically stable at 2–8 °C for at least 4 years. Stability studies are ongoing.

7.3 Final formulation

The co-formulation of spray-dried YF476 and HPMC is blended with starch, and placed into hard gelatine capsules at the Hammersmith Medicines Research (HMR) Pharmacy. Each capsule contains 25 mg YF476. Matching placebo capsules, containing starch only, will also be prepared. The sponsor will provide a certificate of analysis for the test product.

7.4 Packaging and labelling

For the CUMC, HMR Pharmacy will provide bulk supplies of investigational medicinal product (IMP) in accordance with The Rules Governing Medicinal Products in the European Union, Volume 4: Good Manufacturing Practice (GMP)¹⁹, and with HMR's Manufacturing Authorisation for IMPs (MIA(IMP)). The trial medication will be dispensed and labelled by the site pharmacy in accordance with United States Code of Federal Regulations governing labelling of investigational new drugs (21CFR 312.6).

For NIHR CIW, the trial medication will be packaged and labelled by the HMR Pharmacy, in accordance with The Rules Governing Medicinal Products in the European Union, Volume 4: Good Manufacturing Practice (GMP)¹⁹, and with HMR's Manufacturing Authorisation for IMPs (MIA(IMP)). The IMP labels will include the information required by Annex 13 to GMP.

7.5 Storage, accountability and dispensing of study medication

The HMR Pharmacy will dispatch the study medication to the site Pharmacy by secure temperature-controlled courier after ethical and regulatory approvals of the trial have been obtained. The site Pharmacy will record and acknowledge in writing the receipt of all supplies of study medication. The study medication will be stored securely at 2 to 8°C, protected from moisture and light, accessible only to those individuals authorised by the investigator to dispense the IMP.

Each site pharmacy will dispense study drug (or placebo) for trial patients in accordance with the randomization code. The labels on bottles given to trial patients will not indicate whether the capsules are study drug or placebo, so as to maintain blindness among the study investigators and study patients.

The site Pharmacy will maintain a careful record of the inventory and disposition of all medication received from the HMR Pharmacy. The site Pharmacy will maintain adequate records of receipt, dispensing and final disposition of YF476 and placebo. The receipt record will include from whom the study medication was received and to whom

study medication was distributed, date, quantity and batch or lot number. The dispensing record will be blinded, and will include quantities and the dates YF476 or placebo was dispensed to and returned by each participant. [name] will be responsible for study medication accountability for participants at CUMC and [name] will be responsible for study medication accountability for participants at NIHR CIW.

At the end of the trial, all unused study medication supplies will be returned to the HMR Pharmacy.

7.6 Registration and randomization

- A member of the HMR Statistics and Data Management Department will generate a randomization list for each site. Patient numbers will be allocated to eligible patients immediately before the EGD and biopsy at Visit 2 (Baseline). Patients enrolled at CUMC will be allocated patient numbers 01–24. Patients enrolled at NIHR CIW will be allocated patient numbers 1001–1024. The lists are independent of each other. At both sites, patients on PPI once daily will be given the next available number from the top of the list, and patients on PPI twice daily will be given the next available number from the bottom of the list.
- At each site, the site coordinators will maintain a site-specific list of participants, including patient codes, start date, and duration of treatment. Every time a patient is recruited at one of the sites, the coordinator for that site will inform the chief investigator (if applicable) and the coordinator for the other site. It is the chief investigator's responsibility to ensure that the total number of study patients does not exceed the target.

The randomization list will specify whether the patient receives a dose of YF476 or placebo. Fixed allocation randomization will be performed, with equal allocation (1:1) between the 25 mg YF476 and placebo groups. Blocked randomization will be used. Randomization will be stratified by PPI dose and by site. The site pharmacy will dispense YF476 or placebo according to the randomization list. The study investigators and the study patients will remain blinded.

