5.1 Inclusion criteria

1. Aged ≥ 18 years, with histologically confirmed diagnosis of BE, defined as endoscopically-suspected BE with intestinal metaplasia present on esophageal biopsies, without dysplasia. A prior endoscopy with biopsies read as indefinite for dysplasia is permitted if biopsies from the most recent endoscopy prior to study entry demonstrated BE without dysplasia. The most recent endoscopy documenting BE must have been performed no more than three (3) years from the time of enrollment.
2. Minimum of 1 cm circumferential Barrett's mucosa on endoscopy or at least 2 cm maximal contiguous extent of Barrett's mucosa. (Prague criteria $C \geq 1$, any M or any C, $M \geq 2$).
3. Proton pump inhibitor use at least once daily, for at least twelve months prior to enrollment, and stable dose of PPI for the three months before enrollment. Any PPI, dose, and frequency are allowable.
4. ECOG performance status ≤ 2 and Karnofsky $\geq 60\%$; see Appendix A.
5. Participants must have normal organ and marrow function, defined as white blood cells (WBC) $\geq 3 \times 10^9/L$, absolute neutrophil count $\geq 1.5 \times 10^9/L$, platelets $\geq 100 \times 10^9/L$, creatinine ≤ 1.5 mg/dL, total bilirubin ≤ 1.5 mg/dL, AST ≤ 100 U/L, ALT ≤ 100 U/L.

6. The effects of YF476 on the developing human fetus at the recommended therapeutic dose are unknown. All patients must agree to use adequate contraception for the duration of study participation as follows.
 - Pre-menopausal women must use a highly effective method of contraception ($\leq 1\%$ failure/year when used correctly), including:
 - intrauterine device (IUD);
 - bilateral tubal occlusion;
 - vasectomised partner – must have had medical assessment of successful surgery;
 - intrauterine hormone-releasing system (IUS);
 - progestogen-only hormonal contraception implants associated with inhibition of ovulation; or
 - hormonal contraception associated with inhibition of ovulation (combined or progestogen-only – includes oral, intravaginal, transdermal and injections).
 - To prevent pregnancy, men with partners of childbearing potential must use a condom or have had a vasectomy. Partners who are not of childbearing potential are defined as: men; post-menopausal women (no menstrual periods for at least 1 year); or women who have no uterus, ovaries or fallopian tubes.
 - Women classed as post-menopausal (no menstrual periods for at least 1 year) are not required to use contraception.

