13.4 Efficacy Analyses

All efficacy analyses, summaries and listings will be generated using the efficacy analysis set.

Primary efficacy variables are:

- Change in Ki67 expression (ΔKi67)

Secondary efficacy variables are:

- Changes in gene expression in BE tissue (measured by RNA-Seq).
- Change in CCK2R mRNA levels (measured by qRT-PCR)
- Change in DCAMKL1 expression (measured by IHC)
- Change in DCAMKL1 mRNA levels (measured by qRT-PCR)
- Change in COX-2 mRNA levels (measured by qRT-PCR)
- Change in p53 expression (measured by IHC)
- Change in serum gastrin and plasma CgA between baseline and Visit 5

For all efficacy variables listed above, individual values will be presented by patient and summarised by visit.

The primary endpoint (Change from baseline (Visit 2) in Ki67 expression (Δ Ki67)) will be summarised using descriptive statistics. The primary analysis for the primary endpoint will use two sample t-tests comparing between treatment groups. Nominal p-value and 95% confidence intervals for treatment difference will be reported.

To evaluate the robustness of the primary analysis, the following sensitivity analysis will also be performed:

Baseline Adjusted Analysis: this sensitivity analysis will use an analysis of covariance model with the primary endpoint as the dependent variable, treatment group as a factor and baseline (Visit 2) as a covariate. Adjusted least square means and corresponding 95% confidence interval will be reported.

Serum gastrin and chromogranin A (CgA) will be measured at baseline (Visit 2) and at Weeks 6 and 12. Analyses will be performed to determine whether there is a correlation between baseline gastrin and subsequent Δ Ki67. YF476 assays will be performed at Weeks 6 and 12.

Analysis of the secondary endpoints will be similar to the primary analysis. No sensitivity analysis is planned for these endpoints.

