### **3 Introduction**

This Statistical Analysis Plan (SAP) is based on the current trial protocol (version 24, 26 April 2018). Where statistical methods differ substantially between this SAP and the protocol, that will be identified in this document.

This SAP describes the datasets and the statistical methods to be used for the reporting and analysis of all data collected during the trial except the efficacy data which will be reported separately. Serum gastrin and plasma CgA data will be included in this SAP.

The randomisation code will not be broken before this SAP is finalised. If a future protocol amendment necessitates a substantial change to the statistical analysis of the trial data, this SAP will be amended accordingly. If, after database lock, additional analyses are required to supplement the planned analyses described in this SAP, those unplanned analyses will not be described in an amended SAP, but they will be identified in the integrated clinical study report (CSR). Any deviations from this SAP will be documented in the CSR.

This SAP has been written in consideration of the following guidelines:

- International Conference on Harmonization (ICH) E9, Guidance for Industry: Statistical Principles for Clinical Trials (ICH E9 1998); and
- ICH E3, Guidance for Industry: Structure and Content of Clinical Study Reports (ICH E3 1995).

Statistical analysis will be done using SAS® 9.3 on a Windows PC.

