### **13.3 Baseline Characteristics and Concomitant Medication**

Demographic and baseline characteristics (e.g. , vital signs and ECGs) will be listed and summarised.

Patients who take concomitant medication will be listed and summarised.

Proton Pump Inhibitor use data will be listed.

Medical history including history of Barrett's Esophagus data will be listed and summarised

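### Randomisation is labelled as stratified by PPI dose but works by PPI frequency within site, some eligible frequencies have no allocation rule, and the planned Ki67 analyses use neither stratification factor

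*Protocol*

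**What the plan says.** **Eligibility.** Protocol 5.1, criterion 3, requires a PPI at least once daily and adds: "Any PPI, dose, and frequency are allowable".

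**Allocation.** Protocol 7.6 states: "Randomization will be stratified by PPI dose and by site". It describes one independent list per site. Once-daily PPI users take numbers from the top, and "patients on PPI twice daily will be given the next available number from the bottom of the list". Milligram dose, choice of PPI and other frequencies play no part.

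**Analysis.** Protocol 13.4 states: "The primary analysis for the primary endpoint will use two sample t-tests comparing between treatment groups". The one sensitivity analysis is an ANCOVA with "treatment group as a factor and baseline (Visit 2) as a covariate". For the other endpoints, "Analysis of the secondary endpoints will be similar to the primary analysis". No model contains PPI frequency or site.

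**SAP.** The SAP covers all data "except the efficacy data which will be reported separately", but keeps serum gastrin and CgA. It plans no formal testing (4.3) and summarises those two markers by treatment and visit (15). On PPI exposure, SAP 13.3 says: "Proton Pump Inhibitor use data will be listed". Listing 16.2.4.4 has columns for treatment, PPI frequency and dose. Site is used in disposition Table 10.1.

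**The concern.** Two separate things are at stake.

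The first is the accuracy of the design statement. A study report that repeats the label in 7.6 would claim balance on PPI dose when the procedure balances frequency only. Someone allocating an eligible patient who takes a PPI more than twice daily would find no instruction.

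The second is efficiency. Restricted allocation reduces the true sampling variance of the treatment difference when the strata are prognostic. A t-test that ignores the strata still counts the between-stratum variation as error, so its interval is wider than it need be and its test is conservative. PPI exposure is not an arbitrary factor here. Protocol 1.1 and 3.3 present PPI-induced hypergastrinaemia acting through the CCK2 receptor as the pathway under study, and two secondary endpoints are defined as effects on PPI-induced changes.

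**Working it through.** **1. Label against mechanism.** Setting 5.1 beside 7.6:
- Two once-daily users on different doses share a stratum.
- The same total daily dose, taken once or split in two, falls in different strata.
- A patient taking a PPI more than twice daily is eligible and has no stratum.

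**2. Where the factors appear later.** PPI frequency and dose are in Listing 16.2.4.4 and in no summary table. The demographic shell has no PPI row, and the concomitant medication shell counts by generic name without dose or frequency. Site is in Table 10.1. Neither factor is in any model.

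**3. Reproducing the plan's power (Protocol 13.7, Table 1).** Inputs: two-sided 0.05, n = 10 per arm, SD 14–18 points, differences 25–35 points. Power is taken from the noncentral t with 18 df and noncentrality d / (SD × √(2/n)).
- d = 30, SD = 16: 30 / (16 × √0.2) = 4.19; power 97.7% (stated 98%).
- d = 25, SD = 14: power 96.5% (stated 97%).
- d = 25, SD = 18: 25 / (18 × √0.2) = 3.11; power 83.6% (stated 84%).

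All nine cells agree within rounding, so the stated power is that of an unadjusted two-sample t-test.

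**4. Effect of adjustment on the CI.** Let R² be the share of within-arm variance in change in Ki67 explained by PPI frequency and site. The documents give no value, so 0 to 0.3 is an assumed range. Two main effects cost 2 df (18 to 16). With exact balance within strata:

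ratio of half-widths = (t₁₆ / t₁₈) × √(1 − R²) = (2.120 / 2.101) × √(1 − R²)

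| Assumed R² | Ratio | Half-width at SD 16: unadjusted → adjusted (points) |
|---|---|---|
| 0 | 1.009 | 15.0 → 15.2 |
| 0.1 | 0.957 | 15.0 → 14.4 |
| 0.2 | 0.903 | 15.0 → 13.6 |
| 0.3 | 0.844 | 15.0 → 12.7 |

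Break-even is R² = 1 − (t₁₈ / t₁₆)² = 0.018, or 0.028 if all four PPI-by-site cells are fitted (15 df). A separate simulation with permuted blocks of 4 and 40% twice daily (both assumed) gave 14.9 → 15.2 at R² = 0, about 2% wider, because balance is then not exact.

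**5. Type I error and power.** Simulation: 40,000 trials per setting, 20 patients, four cells of 6/4/6/4 (assumed) balanced 1:1; t-test against a linear model with treatment, site and PPI frequency. The null was run at SD 16.

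| R² | Type I error, t-test | Type I error, adjusted | Power d 25, SD 18: t-test / adjusted | Power d 30, SD 16: t-test / adjusted |
|---|---|---|---|---|
| 0 | 0.050 | 0.050 | 83.5 / 82.9% | 97.7 / 97.6% |
| 0.1 | 0.038 | 0.049 | 84.3 / 86.6% | 98.3 / 98.6% |
| 0.2 | 0.028 | 0.049 | 85.3 / 90.3% | 98.6 / 99.3% |
| 0.3 | 0.020 | 0.051 | 86.4 / 93.5% | 98.9 / 99.7% |

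**6. Limit of the calculation.** The adjusted model has no baseline Ki67 term. The gain from adding the strata to an ANCOVA that already contains baseline was not computed and could be smaller.

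**The case against.** The strongest reply is that nothing shows the strata to be prognostic for the endpoint. Patients have at least 12 months of PPI use and a stable dose for three months before enrolment. A steady PPI effect on Ki67 would be present at both biopsies and would tend to cancel in the change. The r = 0.64 between gastrin and Ki67 in Protocol 3.3 is cross-sectional, in ten patients, and concerns level rather than change. The stated mechanism might equally mean that PPI intensity modifies the response to the drug, which is not the main-effect R² assumed here. Protocol 13.4 already plans to correlate baseline gastrin with change in Ki67. In a 20-patient pilot with small cells, leaving out two terms is a defensible choice.

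Most of this stands. It makes the efficiency argument conditional, and it rules out some stronger readings that a reader might infer:
- *That precision is certainly lost.* The documents give no R², and do not say that the stratification was meant to gain precision rather than balance.
- *That the primary test is invalid.* It is at worst conservative.
- *That a PPI imbalance could not be seen.* Listing 16.2.4.4 shows frequency and dose per patient, and SAP 11.1 sorts listings by treatment. With about 20 rows an imbalance can be found; a table would make it plain.
- *That both factors vanish after randomisation.* Site is in Table 10.1.
- *That the SAP's silence on strata for Ki67 is itself a fault.* The SAP defers those data to a separate report, so the point rests on Protocol 13.4.

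The reply does not answer the mismatch between label and mechanism, the missing allocation rule, or the small cost of adjustment relative to its possible gain.

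**Conclusion.** The mismatch in 7.6 is a matter of text and depends on no assumption: the factor used is PPI frequency, not dose, and the two named frequencies do not cover everyone whom criterion 3 admits.

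Omitting the strata from the Ki67 models is a missed low-cost improvement, not an error of validity. Its size depends wholly on the assumed R². The unadjusted interval is near-optimal if R² is below about 0.02–0.03, and is unnecessarily wide above that. At the protocol's headline scenario the power consequence is negligible. It becomes noticeable only in the least favourable Table 1 cell, and only if the strata explain a fair share of the variance. The argument for acting is the asymmetry between a 1–2% loss and a possible gain of 4–16% in CI width over R² of 0.1 to 0.3.

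**What to change.** 1. **Model.** Before unblinding, add PPI frequency stratum and site as factors to the between-arm model for change in Ki67, in Protocol 13.4 or in the separate efficacy plan. Adding them only to the baseline-adjusted ANCOVA improves a sensitivity analysis and leaves the primary t-test as it is, so the primary comparison must also be changed if the gain is to reach it. Do the same for any between-arm gastrin or CgA comparison made under 13.4. If the terms are left out, give the reason. Cost: two degrees of freedom.

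2. **Label.** Reword the factor in 7.6 as PPI frequency, once daily versus more than once daily, or otherwise reconcile label and mechanism so that every eligible patient has a stratum. If patients on other frequencies have already been allocated, record how this was done. Cost: wording.

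3. **Table.** Summarise PPI frequency and total daily dose by arm in a baseline table, in addition to Listing 16.2.4.4. Cost: one table from data that the listing already holds.
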